1.2.4.2 Ibrutinib Resistance in CLL

[figure not shown]
A major limitation of ibrutinib as a CLL therapy is that many patients with CLL will stop responding to ibrutinib either by developing transformation to large-cell lymphoma (Richter's syndrome) or by progressive disease due to resistance to ibrutinib therapy. Relapses as Richter's syndrome tend to occur early and are rare after >2 years of ibrutinib treatment but the risk of progressive CLL increases over time ([Maddock et al 2015](#), [Woyach et al 2017](#)). An analysis of 308 patients who received ibrutinib as participants in clinical trials and followed for a median of 33 months (range 4-61), revealed a cumulative incidence of ibrutinib discontinuation for progressive CLL of 0.7% (95% CI: 0-1.6%) at 1 year and 19.1% (95% CI: 13.9-24.3%) at 4 years ([Woyach et al 2017](#)). As ibrutinib is dosed indefinitely, the number of patients with progressive CLL during ibrutinib therapy is expected to increase over time.

Furthermore, survival for patients discontinuing ibrutinib due to CLL progression was short 22.7 months (95% CI 13.5-NR) and associated with a clinically aggressive disease phenotype ([Woyach et al 2017](#)).

CLL progression due to ibrutinib resistance can be mediated by at least two separate mechanisms: mutations in BTK (BTK^{C481S}) which decreases the affinity of ibrutinib for BTK and changes its binding from irreversible to reversible, and mutations in the immediate downstream target of BTK, PLC γ 2 ([Woyach et al 2014b](#)). These mutations appear during the course of treatment and are not seen in patients who were never exposed to ibrutinib. Once they

are detected on two separate occasions they do not disappear and patients invariably relapse (Maddocks et al 2015, Albistar et al 2015, Albistar et al 2017, Liu et al 2015, Woyach et al 2014b). In ibrutinib-treated patients with a detectable mutation in BTK or PLC γ 2 at time of relapse, a clone with the mutation could be detected in 18/20 patients prior to clinical relapse at a median of 9.3 (95% CI: 7.6-11.7) months before clinical progression (Figure 1-1).

Figure 1-1 Ibrutinib resistance mutations can be detected prior to clinical relapse

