2.7 Rationale for Public Health Emergency mitigation procedures

During a Public Health emergency as declared by Local or Regional authorities i.e. pandemic, epidemic or natural disaster, mitigation procedures to ensure participant safety and trial integrity are listed in relevant sections. Notification of the Public health emergency should be discussed with Novartis prior to implementation of mitigation procedures, and permitted/approved by Local or Regional Health Authorities and Ethics Committees as appropriate.

[figure not shown]
[REDACTED]

3 Objectives and endpoints

Objectives and related endpoints are described in [Table 3-1](#) below.

Table 3-1 Objectives and related endpoints

Objective	Endpoint	Analysis
Primary		Refer to Section 10.4
To determine the MTD and/or RD of the combination of VAY736 with ibrutinib	Safety Escalation only: 
Incidence of DLTs in cycle 1 (28 days) Escalation and expansion: 
Incidence and severity of AEs and SAEs, including changes in laboratory parameters and vital signs Tolerability Dose interruptions, reduction, and dose intensity	
To characterize the safety and tolerability of the combination of VAY736 and ibrutinib		Refer to Section 10.5
Secondary		
To assess any preliminary antitumor activity of the combination	Rate of patients with CR as assessed by investigators per IWCLL at cycle 9 day 1 Overall response rate (ORR) assessed by investigators per IWCLL criteria and Time To Progression (TTP) Clearance of ibrutinib resistance mutations (BTKC481 and/or PLC γ 2 hotspot), defined as less than 1% mutation bearing alleles (Arm B only).	
To characterize the PK of VAY736 and ibrutinib when used in combination therapy	Plasma concentration of VAY736 and ibrutinib, and derived parameters	
To assess immunogenicity (IG) following one or more intravenous infusions of VAY736	Presence of anti-VAY736 antibodies	

Objective	Endpoint	Analysis

[figure not shown]
4 Study design

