10.5.2 Other secondary efficacy objectives

All efficacy analyses are based on FAS.

Rate of CR at C9 for expansion arm A and arm B: The proportion of patients with CR, assessed by investigators per IWCLL criteria (see [Appendix 1](#) for details) at C9 will be provided. The rate of CR at C9 is the primary endpoint for the evaluation of anti-tumor activity and will be analyzed for each expansion arm using a Bayesian modeling approach.

A minimally informative beta distribution is used as prior distribution with parameters $a=0.25$ and $b=1$. This assumes *a priori* response rate of 20%.

Posterior summaries for CR rate (posterior mean, including 90% credible intervals and the posterior probability that the true CR rate falls in the activity intervals defined below) will be provided:

Posterior probability of response rate intervals:

- [0, 20%) – clinically not meaningful
- [20%, 40%) – moderate clinical benefit
- [40%, 100%) – superior clinical benefit

In addition, exact confidence interval (90% CI) also will be provided.

Clearance of ibrutinib resistance mutation for expansion arm B is defined as less than 1% mutation bearing alleles (BTKC481 and/or PLC γ 2) during treatment. The proportion of patients with negative mutation will be provided along with corresponding 90% exact confidence interval (CI).

Overall response rate (ORR) is defined as best overall response (BOR) of complete response (CR) or partial response (PR), assessed by investigators per IWCLL criteria (see [Appendix 1](#) for details). ORR for each expansion arm along with corresponding 90% exact confidence interval (CI) will be provided.

Time to progression (TTP) is the time from start of treatment to the date of event which is defined as the first documented progression or death due to underlying cancer. If a patient has not had an event, time to progression is censored at the date of last adequate disease assessment.

TTP will be described using Kaplan-Meier methods and appropriate summary statistics. .

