2.8 Analysis of other secondary objective(s)

2.8.1 Efficacy analysis

Evaluation of anti-tumor activity will be based on investigators' assessment per IWCLL criteria (see VAY736Y2102-CSP-Appendix 1 for details) as documented in the eCRF. The variables used to evaluate anti-tumor activity are CR/CRi rate, clearance of ibrutinib resistance mutations, overall response rate (ORR), and time to progression (TTP). Analyses of these variables will use the FAS, including patients from both the escalation and expansion parts. All analyses will be provided by dose level in dose escalation and by two arms in dose expansion.

Rate of CR/CRi at C9 for expansion arm A and arm B: The proportion of patients with CR or CRi assessed by investigators per IWCLL criteria (see VAY736Y2102-CSP-Appendix 1 for details) at C9 will be provided. The rate of CR/CRi at C9 is the primary endpoint for the evaluation of anti-tumor activity and will be analyzed for each expansion arm using a Bayesian modeling approach.

A minimally informative beta distribution is used as prior distribution with parameters $a=0.25$ and $b=1$. This assumes, *a priori*, that the response rate is 20%.

Posterior summaries for CR/CRi rate (posterior mean, including 90% credible intervals and the posterior probability that the true CR/CRi rate falls in the activity intervals defined below) will be provided:

Posterior probability of response rate intervals:

- [0, 20%] – clinically not meaningful
- [20%, 40%] – moderate clinical benefit
- [40%, 100%] – superior clinical benefit

In addition, exact confidence interval (90% CI) also will be provided.

To determine which response assessments occurred at C9, response assessment dates within a window of +/- 3 days of patient's Cycle 9 visit start date or end date will be considered as C9 responses.

Clearance of ibrutinib resistance mutation for expansion arm B is defined as less than 1% mutation bearing alleles (BTKC481 and/or PCL γ 2) during treatment (up to C9). The proportion of patients with negative mutation, where negative mutation is defined as having clearance of the baseline ibrutinib resistance mutation, will be provided along with corresponding 90% exact confidence interval (CI). Note that only R665, S707, A708 and L845 variants will be considered as functional PLC γ 2 mutations. Other PLC γ 2 variants will not be considered for this analysis.

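### SAP 2.8.1 counts a patient as mutation-negative when the baseline mutation clears, even if another listed BTK or PLCγ2 resistance variant stands at 1% or more

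*SAP*

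**What the plan says.** Protocol Table 3-1 lists the secondary endpoint as "Clearance of ibrutinib resistance mutations (BTKC481 and/or PLC γ 2 hotspot), defined as less than 1% mutation bearing alleles (Arm B only"). Protocol 10.5.2 repeats the threshold: "Clearance of ibrutinib resistance mutation for expansion arm B is defined as less than 1% mutation bearing alleles", and adds "The proportion of patients with negative mutation will be provided along with corresponding 90% exact confidence interval (CI"). Neither place restricts the count to the mutation found at baseline, and neither says what negative means beyond the 1% threshold.

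SAP 2.8.1 makes this more specific in three ways:

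- Period: clearance "is defined as less than 1% mutation bearing alleles (BTKC481 and/or PCL γ 2) during treatment (up to C9").
- Numerator: "negative mutation is defined as having clearance of the baseline ibrutinib resistance mutation".
- Loci: for PLCγ2 only R665, S707, A708 and L845 count as functional, and "Other PLC γ 2 variants will not be considered for this analysis".

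In the same section the CR/CRi endpoint is tied to a visit: "To determine which response assessments occurred at C9, response assessment dates within a window of +/- 3 days" of the Cycle 9 visit dates qualify. Clearance has no comparable rule.

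The legible part of SAP Section 4 (changes to protocol-specified analyses) does not mention the restriction to the baseline mutation. One item there is redacted, but it refers to SAP 2.9.5. Another is cut short, but it concerns the CR rate.

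**The concern.** Protocol 2.1 gives removal of CLL cells with acquired ibrutinib resistance as one of the hopes for the combination. Protocol 1.2.4.2 explains that "CLL progression due to ibrutinib resistance can be mediated by at least two separate mechanisms", naming BTK and its immediate downstream target PLCγ2. If one resistant clone shrinks and another takes its place, the patient still carries ibrutinib resistance in the sense of the protocol's own rationale. The SAP numerator does not look for this and scores the patient as a success.

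At stake is the interpretation of the only molecular efficacy endpoint listed for Arm B in Table 3-1. A reader would take the mutation-negative proportion to mean patients without detectable resistance at the 1% level. As defined, it means patients whose original clone fell below 1%, whatever else was found.

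**Working it through.** The documents give no expected rate, power or sample-size figure for clearance, so there is no plan figure to reproduce. The check applies the definition to cases and then bounds the effect.

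**Inputs**
- Threshold: below 1% (SAP 2.8.1; Protocol Table 3-1 and 10.5.2).
- Loci: BTK C481 and four PLCγ2 variants (SAP 2.8.1).
- Planned size: about 20 in Arm B (SAP 2.1 and 3.1.2). Enrolment closed early (Protocol Amendment 06; SAP 1.1), and the final number is not given.
- Tests up to C9: Protocol Table 7-2 (Q4W) shows C7 and C9, and by column position C4, so up to three. The row cannot be read in the available text of Table 7-1 (Q2W); this is not treated as an omission.
- Arm B entry: variant allele frequency of at least 1%, or below 1% and rising on two measurements (Protocol 5.2, criterion 6b).

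**Step 1. Apply the definition to hypothetical records**

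| Baseline | On treatment | SAP 2.8.1 | All listed variants below 1%, same sample |
|---|---|---|---|
| BTK C481 at or above 1% | BTK 0.4%, new PLCγ2 R665 at 6% | Negative | Not negative |
| BTK C481 and PLCγ2 L845 both at or above 1% | Only one falls below 1% | Not settled (and/or) | Not negative |
| BTK C481 at or above 1% | Below 1% at C4, at or above 1% at C9 | Not settled (no visit rule) | Depends on the visit; not negative at C9 |
| Rising but below 1% | Below 1% throughout | Not settled; threshold already met at entry | Needs its own rule |

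Only the first row follows directly from the SAP wording. The other three show gaps.

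**Step 2. Direction**
Fix the visit. Let A be the patients whose baseline mutation is below 1%, and B those with every listed variant below 1%. When the baseline mutation is one of the listed variants, every member of B is in A. So

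p(SAP) − p(all variants) = k/N ≥ 0,

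where k is the number who clear the baseline clone but carry another listed variant at 1% or more.

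**Step 3. Size per patient**
- N = 20: 1/20 = 5 points.
- N = 10 (assumed): 1/10 = 10 points.
- N = 5 (assumed): 1/5 = 20 points.

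The documents give no information on k. For scale, the exact (Clopper-Pearson) 90% CI for 4/20 is 7.1% to 40.1%, a width of 40.1 − 7.1 = 33.0 points, so one patient is small against sampling error at the planned size. At N = 5, moving from 1/5 to 2/5 shifts the interval from 1.0%–65.7% to 7.6%–81.1%.

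**Step 4. Why the visit should be stated**
Suppose a patient who has not truly cleared reads below 1% with probability q at each test, independently (both are assumptions). Under a C9-only rule the patient counts with probability q. Under an any-of-three rule the probability is 1 − (1 − q)³:
- q = 5%: 1 − 0.95³ = 14.3%.
- q = 10%: 1 − 0.90³ = 27.1%.
- q = 20%: 1 − 0.80³ = 48.8%.

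This compares two possible rules. It does not show that the SAP adopts the second.

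**The case against.** The strongest reply is that following the qualifying clone is a coherent choice. Patients enter Arm B because of a particular mutation, so asking whether the combination reduces that clone measures activity against it, and CR/CRi, ORR and TTP are reported separately. That stands as a reason to keep baseline-clone clearance in the report. It does not justify labelling it mutation-negative, nor narrowing the protocol endpoint without listing the change.

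A second reply is that the derivation may be completed in the programming specifications, output shells or laboratory manual, none of which is available here. That is possible, but the SAP sentence is explicit and those documents should follow it.

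A reader might also go further than the text allows:
- That one low reading at any visit is enough. The SAP names no visit and requires no confirmation, but it does not say that a single test suffices.
- That a patient with both mutations counts after clearing one, or after clearing each at a different visit. The and/or wording can equally mean that alleles bearing either or both mutations must be below 1%, and nothing describes combining genes across visits.
- That the proportion is inflated by some stated number of points. The documents do not give the share of patients with dual or emergent mutations. Protocol 1.2.4.2 says these mutations do not disappear once detected on two occasions, so clearance of the baseline clone may itself be rare.

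These remain ambiguities to settle, not established errors.

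**Conclusion.** The concern holds for emergent or other coexisting variants: under SAP 2.8.1, clearing the baseline mutation makes a patient negative even with a different listed variant at 1% or more in the same sample. This is narrower than the protocol endpoint and is not declared in the legible part of SAP Section 4. Relative to an all-variants rule at the same visit it can only raise the proportion; that direction assumes the baseline mutation is one of the listed variants. The total effect cannot be estimated.

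The treatment of dual baseline mutations, the visit that counts, and entrants already below 1% are unspecified. Two programmers could reasonably produce different proportions.

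The consequence is limited. This is a descriptive secondary endpoint with no hypothesis or decision rule, in one arm closed for slow enrolment, in a trial the SAP says was endorsed for early termination. It should still be corrected, because the reported label would not match what was counted.

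**What to change.** In SAP 2.8.1:

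1. Define mutation-negative as BTK C481 and all four listed PLCγ2 variants, whether present at baseline or emergent, each below 1% in the same sample. This also settles the dual-mutation case.
2. State the visit, for example C9 with a date window as for CR/CRi, or state a persistence rule.
3. Report separately the patients who clear the baseline clone but carry another listed variant at 1% or more. Baseline-clone clearance then remains visible.
4. State how patients who entered Arm B with a rising allele frequency below 1% are handled, for example as not evaluable for clearance or on their own row.
5. Record the definition in SAP Section 4. SAP Section 1 provides the route: an amendment before database lock or an addendum after it.

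The cost is a few sentences and one extra table row, and the reported proportion may be slightly lower. No new tests should be needed where the resistance-mutation schedule in Protocol Table 7-2 applies; confirm the same for the Q2W schedule.

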2.8.2 Safety analyses

The Safety Set will be used for summaries and listings of safety data with the exception of dose limiting toxicities (DLTs) for which the DDS will be used.

2.8.2.1 Adverse events (AEs)

2.8.2.1.1 Data handling and AE date imputation rules

Adverse events will be coded using the Medical Dictionary for Regulatory Activities (MedDRA) and assessed according to the Common Terminology Criteria for Adverse Events (CTCAE) version 4.03, respectively.

The CTCAE represents a comprehensive grading system for reporting the acute and late effects of cancer treatments. CTCAE grading is by definition a 5-point scale generally corresponding to mild, moderate, severe, life threatening, and death. This grading system inherently places a value on the importance of an event, although there is not necessarily proportionality among grades (a grade 2 is not necessarily twice as bad as a grade 1).

If CTCAE grading does not exist for an adverse event, the severity of mild, moderate, severe, and life-threatening, death related to the AE corresponding respectively to Grades 1 - 5, will be used. Information about any deaths (related to an Adverse Event or not) will also be collected through a Death form.

A missing AE start date will be imputed using the following logic matrix described in [Table 2-3](#).

Table 2-3 Imputation rules for a partially missing AE start date

	AEM MISSING	AEM < TRTM	AEM = TRTM	AEM > TRTM
AEY MISSING	No imputation	No imputation	No imputation	No imputation
AEY < TRTY	(D)	(C)	(C)	(C)
AEY = TRTY	(B)	(C)	(B)	(A)
AEY > TRTY	(E)	(A)	(A)	(A)

AEM: Month AE started; AEY: Year AE started

TRTM: Month treatment started; TRTY: Year treatment started

[Table 2-4](#) is the legend to the logic matrix shown in [Table 2-3](#) and details the relationship of AE start date to study treatment start date.

Table 2-4 Imputation legend and AE/treatment start date relationship

	AE start date relationship	Imputation
(A)	After treatment start or Uncertain	MAX(01MONYYYY, TRTSTD+1)
(B)	Uncertain	TRTSTD+1
(C)	Before treatment start	15MONYYYY
(D)	Before treatment start	01JULYYYY
(E)	After treatment start	01JANYYYY

Before treatment start: Partial date indicates AE start date is prior to treatment start date.

After treatment start: Partial date indicates AE start date is after treatment start date.

Uncertain: Partial date insufficient to determine relationship of AE start date to treatment start date.

No imputation will be performed for AE end dates.

All events with a start date before or on the cut-off date and end date after the cut-off date will be reported as 'ongoing'. The same rule will be applied to adverse events starting before or on the cut-off date and not having a documented end date. No imputation will be performed for missing/incomplete AE end dates.

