7.1.1 Screening

Screening starts after a patient has provided written informed consent to participate in the study and ends on the day of the first dose of VAY736 and ibrutinib. Screening assessments have to be done within 21 days prior to the first dose with the exception of baseline tumor assessments and informed consent. Screening tumor assessments collection can be conducted within 28 days of first dose and informed consent can be obtained within 3 months of the first dose. Assessments conducted prior to obtaining informed consent as a part of routine disease care can be used to satisfy eligible criteria as long as the procedures were performed within the allowed windows.

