2.3.4.4 Partial-date imputation rules for prior antineoplastic therapies

The following partial-date imputation rules will apply:

Start date:

The same rule which is applied to the imputation of AE/concomitant medication start date will be used, with the exception of the imputation rule in scenario (B) of [Table 2-4](#), which will be replaced by TRTSTD-1. See [Section 2.8.2.1.1](#).

End Date:

Imputed date = min (start date of study treatment, last day of the month), if day is missing;

Imputed date = min (start date of study treatment, 31DEC), if month and day are missing.

If the end date is not missing and the imputed start date is after the end date, use the end date as the imputed start date.

If both the start date and the end date are imputed and if the imputed start date is after the imputed end date, use the imputed end date as the imputation for the start date.

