2.5.2 Prior, concomitant and post therapies

Concomitant therapies are defined as any medications (excluding study treatment, prior antineoplastic treatments) and significant non-drug therapies (including physical therapy and

blood transfusions) administered in the study and are recorded in the Concomitant Medications and Prior or Concomitant non-drug therapies/procedures eCRF. These therapies will be coded using the WHO Drug Reference Listing (WHO DRL) dictionary that employs the WHO Anatomical Therapeutic Chemical (WHO ATC) classification system. Significant non-drug therapies will use MedDRA coding.

Any concomitant therapies starting prior to or after the start of study treatment will be listed.

A separate listing will be provided for instances of concomitant, limited-field palliative radiotherapy to non-target lesion(s). Per protocol VAY736Y2102-CSP-Section 6.4, such concomitant therapies are allowed, and will be recorded on the Concomitant radiotherapy/surgery case report form (CRF) page.

The imputation of a concomitant medication start date will follow the same conventions as for an AE start date (see [Section 2.8.2.1.1](#) for AE date imputation rules). No imputation will be performed for concomitant medication end dates.

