2.8.2.1.2 Data analysis

AE Summaries (CSR outputs)

AE summaries will include only AEs that started or worsened during the on-treatment period, the treatment-emergent AEs. All AEs collected in the AE (e)CRF page will be listed along with

the information collected on those AEs e.g., AE relationship to study drug, AE outcome etc. AEs starting during the post-treatment period will be flagged in the listings.

AEs will be summarized by number and percentage of patients having at least one AE, having at least one AE in each primary system organ class (SOC) and for each preferred term (PT) using MedDRA coding. A patient with multiple occurrences of an AE will be counted only once in the respective AE category. A patient with multiple CTCAE grades for the same preferred term will be summarized under the maximum CTCAE grade recorded for the event. AE with missing CTCAE grade will be included in the 'All grades' column of the summary tables.

In AE summaries the primary system organ class will be presented alphabetically, and the preferred terms will be sorted within primary SOC in descending frequency. The sort order for the preferred term will be based on their frequency in the investigational arm.

The following adverse event summaries will be produced by treatment:

- Overview of adverse events (number and % of patients with any AE, any SAE any fatal SAE, any dose reductions/interruptions, AE leading to discontinuation, AE requiring additional therapy);

The following adverse event summaries will be produced by treatment and maximum grade (All grades and Grade ≥ 3):

- AEs by SOC and PT, regardless of relationship to study treatment and suspected to be related to study treatment;
- Serious adverse events by SOC and PT, regardless of relationship to study treatment and suspected to be related to study treatment Leading to treatment discontinuation;
- AEs leading to dose interruption/adjustment;
- AEs Requiring additional therapy;
- Dose limiting toxicities by SOC and PT;

The following listings will be produced:

- All adverse events (safety set)

Deaths (CSR Outputs)

Separate summaries for on-treatment and all deaths (including post-treatment death) will be produced by treatment arm, system organ class (SOC) and preferred term (PT).

All deaths will be listed for the safety set, and post-treatment deaths will be flagged.

The death summaries cover patients from the Safety Set.

EudraCT and clinicaltrials.gov requirements for AEs and Deaths summaries

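### The AE start-date imputation ignores a known end date, so some events that ended before first dose are classed as treatment-emergent

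*SAP*

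**What the plan says.** SAP 2.8.2.1.1 gives the rule: "A missing AE start date will be imputed using the following logic matrix described in" Table 2-3, with Table 2-4 as its legend. The matrix has two sets of inputs, "AEM: Month AE started; AEY: Year AE started" and "TRTM: Month treatment started; TRTY: Year treatment started". In case (B), the AE year equals the treatment-start year and the AE month is either missing or equal to the treatment-start month. The imputed start is then TRTSTD+1, the day after first dose. The legend calls this case uncertain, meaning "Partial date insufficient to determine relationship of AE start date to treatment start date". The AE end date appears only in the statement that it is not itself imputed. SAP 5.1.2 adds nothing, as it only points back to this section.

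SAP 2.8.2.1.2 then says: "AE summaries will include only AEs that started or worsened during the on-treatment period, the treatment-emergent AEs". SAP 2.1.1.5 defines treatment-emergence by a start date in the on-treatment period, which opens on the day of first dose. It sends incomplete dates to that period only where they leave the period unclear.

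SAP 2.3.4.4 reuses the same matrix for prior antineoplastic therapies, but changes case (B) to TRTSTD-1 and adds a check: "If the end date is not missing and the imputed start date is after the end date, use the end date" as the start. SAP 2.5.2 has no such check for concomitant medications: "The imputation of a concomitant medication start date will follow the same conventions as for an AE start date".

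**The concern.** Defaulting to on-treatment is sensible when nothing shows on which side of first dose an event began. It is not sensible when a complete end date already answers the question. Case (B) judges uncertainty from the partial start date alone. It can therefore give an event a start later than its own recorded end and move a pre-treatment event into the treatment-emergent tables. That departs from the principle in SAP 2.1.1.5 and from the safeguard the SAP uses in 2.3.4.4.

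Such records can arise. Protocol 8.1.1 has AEs recorded from consent onward with both start and end dates, and Protocol 7.1.1 says "informed consent can be obtained within 3 months of the first dose". AE incidence is part of the primary objective (SAP 2.6), so a rule that can only raise the count deserves correction.

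**Working it through.** **Inputs.** The matrix and legend come from SAP Tables 2-3 and 2-4. The treatment-emergent definition comes from SAP 2.1.1.5 and 2.8.2.1.2, and the end-date cap from SAP 2.3.4.4. The plan states no figure to reproduce.

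**Step 1, one record.** Assume first dose 20MAR2021, AE start MAR2021 and AE end 10MAR2021. The year and month match, so case (B) applies. The imputed start is 20MAR2021 + 1 day = 21MAR2021. End minus imputed start = 10 − 21 = −11 days. The imputed start lies in the on-treatment period, so the event is treatment-emergent. With the cap, the start is the earlier of 21MAR2021 and 10MAR2021, which is 10MAR2021 and pre-treatment.

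**Step 2, which cases fail.** Take the example first-dose date in SAP 2.1.1.3, 05-Jan-2014, and assume an AE end of 03-Jan-2014.

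| Partial AE start | Case | Imputed start | Treatment-emergent as written | With cap |
|---|---|---|---|---|
| JAN2014 | B | 06-Jan-2014 | Yes | 03-Jan-2014, no |
| 2014 | B | 06-Jan-2014 | Yes | 03-Jan-2014, no |
| DEC2013 | C | 15-Dec-2013 | No | Unchanged |
| 2013 | D | 01-Jul-2013 | No | Unchanged |
| Year missing | None | None | Not set by the matrix; 2.1.1.5 applies | Not applicable |

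Only case (B) misclassifies.

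**Step 3, all date combinations under an assumption.** Take every first-dose date in 2014, every true AE start 1 to 21 days earlier, and every end from the start to the day before first dose. The 21-day span is an assumption. There are 365 × (1 + 2 + … + 21) = 365 × 231 = 84,315 combinations.

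- *Day missing.* Case (B) applies when the true start is in the treatment-start month. A month of D days gives 1,771 + 231 × (D − 22) combinations, where 1,771 = 21 × 22 × 23 / 6. That is 3,850 for 31 days, 3,619 for 30 and 3,157 for 28. The year gives 7 × 3,850 + 4 × 3,619 + 3,157 = 44,583, or 52.9%.
- *Day and month missing.* Case (B) applies when the true start is in the treatment-start year: 1,771 + 231 × 343 = 81,004, or 96.1%.
- *With the cap.* None remain in either setting.

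These are shares of date combinations, given a partial start and a pre-dose end. They do not predict how many AEs will be affected.

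**Step 4, size per patient.** A patient counts once per AE category (SAP 2.8.2.1.2). In a pooled group of n patients, one affected patient therefore raises a row by at most 1/n: 1/3 = 33 percentage points, 1/6 = 17, 1/20 = 5. These values of n are illustrations.

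**The case against.** The strongest reply is that the trigger is narrow and the error is in the cautious direction. The event must begin after consent, end before first dose, and have a complete end date but a partial start that falls in case (B). Protocol 9.3 and 9.4 provide for automatic data checks and queries, which should catch many such records. Safety output is descriptive, and no planned dosing decision is shown to depend on it. All of this stands, and it limits the impact. It does not make the rule right. Caution is a reason to default when timing is unknown, and here the end date makes it known.

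It can also be said that SAP 2.1.1.5 already covers the case, because a pre-dose end date allows clear assignment. That shows the intent but does not override Table 2-3. Once TRTSTD+1 is filled in, the date is complete and falls on-treatment, and nothing sends the programmer back.

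A reader might infer several stronger points that the documents do not support:

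- *That the rule attributes these events to VAY736 plus ibrutinib.* Treatment-emergence concerns timing. Causality is a separate investigator assessment (Protocol 8.1.1), tabulated separately.
- *That the whole three-month consent window is exposed.* A start in a known earlier month goes to case (C). The wider window matters only when the month is missing too.
- *That an expansion arm of 20 is the denominator.* Safety tables pool by VAY736 dose level and schedule across study parts (Protocol section 10; SAP 2.1).
- *That negative durations distort results.* No AE-duration summary is planned. The only end-to-start arithmetic is the gap rule for registry occurrence counts in SAP 2.8.2.1.2, where an impossible start date would be a faulty input.

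**Conclusion.** Wrong as written, with minor impact. In case (B), an AE with a complete end date before first dose is imputed to start after it ended and is classed as treatment-emergent. Cases (C) and (D) leave such an event pre-treatment. The documents do not say how many AE records have partial starts, so the total effect cannot be computed; it is probably small. Any effect on an AE row is upward. It is at most one count per affected patient, and zero if that patient already has an on-treatment event in the same row. The default for starts whose timing really is unknown is not in question.

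**What to change.** Add to SAP 2.8.2.1.1 the check already in SAP 2.3.4.4: "If the end date is not missing and the imputed start date is after the end date, use the end date" as the imputed start. Because AE end dates are not imputed, say that the check applies to complete end dates. It would not hide on-treatment events: one that ended on the day of first dose would be capped at that day and stay treatment-emergent. A cross-reference to SAP 2.1.1.5 would reconcile the two sections.

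The same check would pass to concomitant medications through SAP 2.5.2. Those are only listed, so there it merely tidies the listing.

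The cost is one sentence and one line of derivation code, made by SAP amendment before database lock or by addendum after it, as the SAP introduction provides.
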